Once Arm B is opened, patients who are eligible for both Arm A and Arm B will be randomised 2:1 to Arm B: Arm A in an open-label manner on Day 1. Randomisation will be stratified by genetic alteration (RNF43, RSPO).

a A baseline (pre-first dose IP) biopsy is a mandatory requirement, except in exceptional circumstances where biopsy is not technically feasible. All patients without a baseline sample must be approved by Sponsor before starting study treatment. The baseline [CC1] can be a 'fresh newly acquired' biopsy or an [CC1] (preferably from the same organ site that 'on treatment' biopsy will be taken) and taken after completion of all prior standard of care treatments. In exceptional circumstances where baseline biopsy cannot be scheduled before C0D1, the procedure may be performed before C1D1 after a minimum of 4 days washout from C0D1. A second 'on treatment' biopsy at Cycle 1 Day 15 (+/- 1 day), is also mandatory providing that investigator judges the second biopsy to be technically and clinically feasible. The Cycle 1 Day 15 biopsy should be collected post-dose and the time of collection should be accurately recorded. RECIST 1.1 target lesions should not be chosen for biopsies.

b [CC1]

c Triplicate ECGs should be collected as follows;

Cycle 0: [CC1]

Cycle 1, [CC1]

Cycle X, [CC1]

At selected sites, ambulatory Holter monitoring will be used on Cycle 0 Day 1 and Cycle 1 Day 15 for central analysis of digital ECG information.

d [CC1]

e [CC1]

[CC1]

f Blood samples for PK analysis should be collected as follows (the actual time for each blood draw must be accurately recorded);  
Cycle 0: CCI  
Cycle 1, CCI  
Cycle X, CCI

g CCI

h ECGs are required at C2D1 and as clinically indicated from C3D1 onwards

i CCI

CCI

CCI

j RXC004 + nivolumab combination treatment will be allowed for up to 20 patients that have progressed on RXC004 monotherapy. This treatment phase will only be opened after the RP2D for RXC004 + nivolumab is determined

k Patients that consent to RXC004 + nivolumab combination treatment will have eligibility re-assessed for RXC004 + nivolumab combination specific criteria

l One 'on treatment' biopsy is required during cycle 3 of RXC004 monotherapy or RXC004 + nivolumab combination treatment, providing that investigator judges the biopsy to be technically and clinically feasible. The biopsy should be collected post-dose and the time of collection should be accurately recorded.

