## **6.6 Dose Modification**

RXC004 dose reduction and interruption are permitted. Nivolumab dose reduction is not permitted but dose interruption/delay is permitted as per Appendix G.

RXC004 may be dose interrupted (withheld) until a clinically significant (any grade) and/or a grade  $\geq 3$  related adverse event resolves to baseline or  $\leq$  grade 2. RXC004 may also be withheld if it is necessary to give a concomitant medication that is a moderate or strong CYP3A4 inhibitor. RXC004 related colitis events should be managed as per Appendix J.

Adverse events that are assessed as being causally related nivolumab should be managed as per the Nivolumab Toxicity Management and Dose Modification Guidelines (Appendix G). If either agent is interrupted or discontinued for a related-AE the other agent (nivolumab or RXC004) may be continued if the patient is judged (by the investigator) to be receiving clinical benefit.

RXC004 and nivolumab dose interruption and stopping criteria are detailed in Table 14.

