### 8.3.2 Follow-up of AEs and SAEs

Any AEs that are unresolved at 90 days after last dose of IP should be followed up by the

investigator for as long as medically indicated, but without further recording in the eCRF. Redx retains the right to request additional information for any participant with ongoing AE(s)/SAE(s) at the end of the study, if judged necessary.

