#### **9.4.3.1 Adverse events**

Treatment emergent AEs (TEAEs) are defined as those AEs with an onset after dosing and those pre-existing AEs that worsen after the start of dosing and within 30 days of stopping RXC004 monotherapy or 90 days after the last actual nivolumab dose (for patients on RXC004 and nivolumab combination). For AEs, verbatim terms in the eCRF will be mapped to preferred terms and system organ class using the Medical Dictionary for Regulatory activities (version 22.0 or later) CTCAE criteria v5.0 will be used to grade the severity of AEs. The incidence of treatment emergent AEs will be summarised by preferred term and system organ class as well as severity. Treatment related TEAEs will be summarised in the same way. Subject incidence of SAEs will also be produced.

By subject listings of all AEs, deaths, SAEs and TEAEs leading to discontinuation will also be produced.

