4.2.3 Definition of Baseline and Post-baseline Assessments

A baseline assessment will be defined as the last assessment performed prior to the first dose of study treatment (C0D1). While many of these assessments will be performed on the day of the first dose, others will be performed during screening. If a patient is missing an assessment typically performed on the day of the first dose, screening values may be substituted as baseline.

Patients treated with RXC004 monotherapy (arm A) that radiologically progress as per RECIST1.1 at the first 'on treatment' scan, may be treated with RXC004 + Nivolumab combination. Accordingly, the following groups of analyses have to be defined to clarify which patients and which information in arm A will be utilized:

- **Arm A (RXC004 monotherapy):** this group will include information for all patients enrolled in arm A.
- **Arm A1 (RXC004 monotherapy):** this group will include information of all patients enrolled in Arm A who were on monotherapy throughout the study - ie. subjects who did not radiologically progressed at the first scan (week 8) or who radiologically progressed

at the first scan (week 8) but remained on monotherapy or who withdrew before the first scan.

- **Arm A2 (RXC004 + Nivolumab):** this group will include information of patients enrolled in arm A who radiologically progressed at the first scan (Week 8) and then switch to receive combination therapy of RXC004 + Nivolumab either at Week 8 or later. The last scan before the switch to combination treatment will be set as the arm A2 baseline RECIST1.1 scan for the combination treatment. The date of the last scan before switching to combination treatment will also be used to determine the arm A2 baseline date for all the efficacy endpoints except OS. OS will keep the same baseline regardless of the progression. For assessments other than efficacy, Arm A2 summaries, will include data from start of monotherapy until end of combination treatment.
- **Arm B (RXC004 + Nivolumab):** this group will include information on all patients enrolled in arm B.

Some patients with symptomatically stable disease may continue treatment after the initial RECIST 1.1 - defined progression, until symptomatic/clinical progression or a second RECIST 1.1 PD assessment (relative to the initial RECIST1.1 progression, for a given study treatment).

Change from baseline is derived where both baseline and post-baseline values are available:

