4.12.1 Adverse Events

Adverse Events will be collected from time of signature of informed consent form throughout the treatment period and until 30 days after the last dose of RXC004 (for patients treated with RXC004 monotherapy only) or 90 days after the last dose of Nivolumab (for patients treated with RXC004 and Nivolumab).

SAEs will be recorded from the time of signing of informed consent form until the follow-up period is completed: 30 days after the last dose of RXC004 (for patients treated with RXC004 monotherapy only) or 90 days after the last dose of Nivolumab (for patients treated with RXC004 and Nivolumab).

The following variables will be collected for each AE:

- AE (verbatim)
- Start/Stop date
- CTCAE grade at onset and grade changes
- Seriousness
- Investigator causality rating against the Investigational Product(s)
- Action taken with regard to Investigational Product(s)
- Action taken with regards to AE

- Outcome

In addition, the following variables will be collected for SAEs:

- Date AE met criteria for SAE
- Date investigator became aware of SAE
- Hospitalisation
- Life Threatening
- Congenital Anomaly or Birth Defect
- Disability or Permanent Damage
- Other Medically Important Serious Event
- Date of hospitalisation
- Date of discharge
- Causality assessment in relation to Study procedure(s)
- Causality assessment to other medication

Partially complete AE dates will not be imputed in the listings and the available day, month and year components will be used to determine if an adverse event is treatment- emergent taking the first dosing date last treatment date as references.

More specifically:

- Start date of AE missing: Assumed to be date of first treatment dose.
- Start day and month of AE missing: Assumed to be date of first treatment dose (if same year for both dates), January 1st otherwise.
- Start day of AE missing: Assumed to be date of first treatment dose (if same month and year for both dates), first day of the month otherwise.
- End date for non-ongoing AE missing: Assumed to date of last treatment dose
- End day and month for non-ongoing AE missing: Assumed to be date of last treatment dose (if same year for both dates), December 31st otherwise.
- End day for non-ongoing AE missing: Assumed to be date of last treatment dose (if same month and year for both dates), last day of the month otherwise.

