Explain if first use TEAEs with missing relationship to the study drug will be considered as related. AEs will be coded using the MedDRA, latest version. Grading will be performed using CTCAE version 5.0.

TEAEs are defined as those AEs with an onset after dosing and those pre-existing AEs that worsen after the start of dosing and within 30 days of stopping RXC004 monotherapy or 90 days after the last actual Nivolumab dose (for patients on RXC004 and Nivolumab combination).

An overview table of TEAEs will be provided showing the number of patients, the percentage of patients and the number of events for the following categories of events:

- Any TEAE
- Any treatment related TEAE to RXC004
- Any treatment related TEAE to Nivolumab
- Any grade ≥ 3 TEAE
- Any grade ≥ 3 TEAE related to RXC004
- Any grade ≥ 3 TEAE related to Nivolumab
- Any serious TEAE (STEAE)
- Any serious TEAE related to RXC004
- Any serious TEAE related to Nivolumab
- Any TEAE leading to death
- Any TEAE leading to permanent discontinuation or reduction or interruption of RXC004
- Any TEAE leading to permanent discontinuation of RXC004
- Any TEAEs leading to RXC004 reduction
- Any TEAEs leading to RXC004 interruption
- Any TEAE leading to permanent discontinuation or interruption of Nivolumab
- Any TEAE leading to permanent discontinuation of Nivolumab
- Any TEAEs leading to Nivolumab interruption

For TEAEs, TEAEs considered related (RXC004 and Nivolumab), STEAEs, STEAEs considered related (RXC004 and Nivolumab), TEAEs leading to study treatment discontinuation, TEAEs leading to RXC004 reduction, TEAEs leading to RXC004 interruption, TEAEs leading to Nivolumab interruption, TEAEs by maximum grade, TEAEs with grade ≥ 3 , TEAEs with grade ≥ 3 related to RXC004, TEAEs with grade ≥ 3 related to Nivolumab, death, detailed tables will be created showing the number of patients who experienced at least one TEAE, the corresponding percentage of patients and the number of events by SOC and PT.

SOC will be sorted by alphabetical order. PTs, within each SOC, will be sorted by descending order of total frequency. In the event of PTs with equal total frequencies, the relevant PTs will be sorted

alphabetically.. In addition, a table summarizing TEAEs by decreasing frequency of Preferred Terms will be produced for all TEAEs and TEAEs related to RXC004/Nivolumab.

A table will also be produced showing the details for every patient that die (death date, cause of death etc...).

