Listing of all AEs (including non-treatment-emergent events) will be provided. This listing will be presented, ordered by arm and patient. It will include patient identifier, AE (SOC, PT, and verbatim term), date of onset, date of resolution, duration, maximum grade, seriousness, action taken, outcome and causality. A listing detailing the serious TEAEs will also be produced.

TEAEs summaries will be conducted for arm A and arm B and separately for arm A1 and arm A2 (in the same table) as applicable.

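### The TEAE window for combination patients ends 90 days after nivolumab even if RXC004 continues alone, and the SAP restricts amylase and lipase to Arm B without declaring it

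*SAP*

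**What the plan says.** **TEAE window.** SAP 4.12.1 defines TEAEs as events that begin after dosing, together with existing events that worsen after dosing starts, and closes the sentence with "within 30 days of stopping RXC004 monotherapy or 90 days after the last actual Nivolumab dose (for patients on RXC004 and Nivolumab combination". Protocol 9.4.3.1 uses the same wording. Neither contains a later-of rule.

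**RXC004 after nivolumab.** Protocol 6.6 states: "If either agent is interrupted or discontinued for a related-AE the other agent (nivolumab or RXC004) may be continued", subject to the investigator's view of clinical benefit. Table 14 says the same for events that require nivolumab to be held and for events that require it to be stopped.

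**Arm A2 (monotherapy patients who switch to the combination).** SAP 4.12.1 says "TEAEs summaries will be conducted for arm A and arm B and separately for arm A1 and arm A2". SAP 4.2.3 says "For assessments other than efficacy, Arm A2 summaries, will include data from start of monotherapy until end of combination treatment".

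**Amylase and lipase.** The chemistry list in SAP 4.12.3 tags both as Arm B only. The same section then promises summaries of every parameter for both arms. Protocol Table 16 lists both tests with no arm restriction; its footnotes concern only creatinine clearance, T3/T4 and screening-only tests. SAP 4.15 does not mention the change.

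**The concern.** Safety incidence is a secondary endpoint, and the TEAE tables are where it is reported. A window tied only to nivolumab suits late immune-mediated events, but it takes no account of continued exposure to the other drug. A patient who stops nivolumab and stays on RXC004 remains under study treatment and under AE collection. Coded as written, the rule would leave that patient's later events out of the SOC and PT tables, and out of overview rows such as TEAEs leading to RXC004 interruption. The Phase 1 combination table (protocol Table 9) tied its TEAE window to 30 days after the last dose of study treatment, so an on-RXC004 event counted there might not count here.

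A combination-arm patient who never reached nivolumab has no anchor at all. This can occur: Arm B takes RXC004 in Cycle 0 before nivolumab starts, and the safety set admits patients given either agent.

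The laboratory restriction matters because the pancreatic signal in Phase 1 arose on monotherapy. Read literally it also excludes switched Arm A patients, so nivolumab exposure does not explain it.

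**Working it through.** The plan states no figure on this point, so there is nothing to reproduce. The check is a day count followed by a comparison of texts.

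**Inputs.** Day 0 is the last nivolumab dose. D is the number of days RXC004 continues after it. D is an assumption shown as a range, because the documents give no value. The 30- and 90-day limits come from SAP 4.12.1.

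**Formulas.**
- End as written (natural reading) = 90
- End under a later-of rule = max(90, D + 30)
- On-RXC004 days outside the window as written = max(0, D − 90)
- All days outside, including 30 days after RXC004 = max(0, D − 60)

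| D | End as written | Later-of end | On-RXC004 days outside | All days outside |
|---|---|---|---|---|
| 28 | 90 | 90 | 0 | 0 |
| 60 | 90 | 90 | 0 | 0 |
| 84 | 90 | 114 | 0 | 24 |
| 90 | 90 | 120 | 0 | 30 |
| 112 | 90 | 142 | 22 | 52 |
| 120 | 90 | 150 | 30 | 60 |
| 168 | 90 | 198 | 78 | 108 |
| 180 | 90 | 210 | 90 | 120 |

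The two rules agree whenever D is 60 or less, which covers patients who stop both drugs at about the same time on a 28-day cycle. They part above 60, and time on drug is lost above 90.

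**Can a patient get there?** Appendix G stops nivolumab permanently for a Grade 2 or 3 event that persists for 12 weeks. If nivolumab was held from onset, at least 12 × 7 = 84 of the 90 days have gone when it is stopped, leaving at most 90 − 84 = 6. Table 14 allows RXC004 to continue in that situation. Other routes are closed: related Grade 4 toxicity stops both drugs, as do Grade 3 or 4 colitis on the combination and colitis that recurs after restarting.

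**Size of one event.** 1/20 = 5 percentage points, using the 20 evaluable patients planned per arm. It is less if the safety set is larger.

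**Arm A2.** SAP 4.2.3 taken literally stops at the end of treatment, while SAP 4.12.1 adds follow-up days. But SAP 4.2.3 also defines Arm A as everyone enrolled in it, and SAP 4.12.1 tabulates Arm A as well as A1 and A2. Protocol 9.4.3 likewise presents the split groups alongside the combined one. A switched patient's post-treatment events therefore still count in the Arm A column.

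**Amylase and lipase.** Protocol Table 4 reports Grade 3 pancreatitis as a DLT in 1 of 6 patients at 2 mg QD, the Arm A starting dose. The Arm A outputs at risk are the by-visit summaries, shift tables and box plots.

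**The case against.** The sentence can be read in ways that lose no on-drug event. The time limit might govern only worsening of existing events, so new-onset events would have no end. Or a patient left on RXC004 alone might fall under the monotherapy limb, which gives D + 30. Both are possible, but the text does not choose. The second has its own cost: at D = 28 the window would end on day 58, earlier than 90. The partial-date rule, "taking the first dosing date last treatment date as references", does not settle the matter because it names no drug.

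The effect may be nil. It needs more than 60 days of RXC004 after nivolumab, and the closed routes above narrow the field further. All AEs are listed whether or not treatment-emergent, RXC004 reductions and interruptions are summarised with reasons, and deaths are tabulated. This stands and limits the size of the point. None of those outputs, however, gives the incidence of a late event by preferred term.

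A reader might infer that SAP 4.2.3 removes follow-up from the safety reporting of all switched patients. The documents do not support that. The sentence sits in a section on baselines, may only describe which treatment phases are covered, and can affect at most the A2 column.

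A reader might also take protocol 8.3.2 as a rival TEAE anchor. It governs follow-up of unresolved events and defines no TEAE window.

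On the laboratory list, the SAP text is loose: it ends in an ellipsis, adds magnesium and urea, and omits TSH. Pancreatitis reported as an AE would still be tabulated. So this is an undeclared inconsistency, and it does not show that Arm A enzymes went unmeasured.

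**Conclusion.** The point holds in three parts of unequal weight.

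1. On its natural reading, the TEAE rule leaves out of the incidence tables any event on RXC004 more than 90 days after the last nivolumab dose. It falls short of RXC004 plus 30 days once RXC004 runs more than 60 days past nivolumab. This rests on reading the nivolumab limb as the only one for combination patients. The number affected is not given and may be zero. It would be tempting to project a share of patients from the PFS that the protocol cites for other agents, but that is not the duration of RXC004 after nivolumab, and the documents offer no basis for it.
2. The Arm A2 wording is a minor inconsistency confined to one column.
3. The amylase and lipase restriction contradicts protocol Table 16 and the SAP's own promise for all parameters, and it is undeclared. Whether Arm A values exist depends on the eCRF, which is not among the documents.

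**What to change.** **SAP 4.12.1.** Define TEAEs as new-onset or worsening AEs from first dose to the later of last RXC004 + 30 days and last nivolumab + 90 days, and to last RXC004 + 30 days where nivolumab was never given.

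**SAP 4.2.3.** Add that Arm A2 TEAE tables use this same window.

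**SAP 4.12.3.** Delete the Arm B restriction on amylase and lipase so that Arm A is summarised. If the values were not captured, declare the departure from protocol Table 16 in SAP 4.15.

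**Cost.** Two sentences, one derivation rule and a few laboratory table rows, applied to data already collected. No new visits are needed: AEs are collected while patients are on treatment, and both schedules already set follow-up at RXC004 (or IP) + 30 days and nivolumab + 90 days. The collection wording in protocol 8.3.1 and 6.7 need not be amended for this. TEAE counts in combination patients may rise slightly or not at all.

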4.12.2 Dysgeusia

Loss of taste (dysgeusia) is an on-target adverse event known to occur with porcupine inhibition. A taste assessment questionnaire will be performed at screening and at each study visit when patient reports dysgeusia.

A bar-chart will present the worst answers to the main questions after screening and a separate one illustrating the worst answers on the way the taste is altered. In the event a patient answering in both directions of ‘more sensitive’ or ‘loss’ then loss will be considered worse. A by-patient listing will also be provided.

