### **8.3.12 Dysgeusia**

Loss of taste (dysgeusia) is an on-target adverse event known to occur with porcupine inhibition (Ng et al 2017, Janku et al 2015). According to CTCAEv5, there are only two grades of dysgeusia;

Grade 1 – Altered taste but no change in diet

Grade 2 – Altered taste with change in diet (e.g., oral supplements); noxious or unpleasant taste; loss of taste.

As dysgeusia is poorly characterized by CTCAE grade alone, site research personnel will complete a taste assessment (consisting of a specific set of questions and an oral examination) at screening for each patient enrolled, and for any patient who reports dysgeusia in response to the open question from the study site staff; 'Have you had any health problems since the previous visit/you were last asked?'. In such cases, the assessment will be performed at each visit until the adverse event has resolved. The information will be recorded and analysed as part of the overall safety objective of the study.

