2 STUDY OBJECTIVES

Objectives	Endpoints
Primary	
To assess the anti-tumour activity of RXC004 monotherapy and RXC004 + Nivolumab	Monotherapy: Disease control rate (DCR) using each patients Best Overall Response (BOR) according to RECIST 1.1 Combination: Objective response rate (ORR) using each patients BOR according to RECIST 1.1
Secondary	
To further assess the preliminary efficacy of RXC004 monotherapy and RXC004 + Nivolumab	% change in the sum of target lesions, duration of response (DoR), PFS, ORR (monotherapy) and DCR (combination) using investigator assessments according to RECIST 1.1 and OS
To assess the PK of RXC004 in monotherapy and in combination with Nivolumab	Maximum plasma concentration (Cmax) after Dose 1, Cmax at steady state, minimum observed plasma concentration (Cmin) at steady state as well as other relevant parameters (e.g. tmax, t ^{1/2} , λz, AUC _{0-∞} , CL/F, and Vz/F)
To assess the safety and tolerability profile of RXC004 monotherapy and RXC004 + Nivolumab combination	Incidence of AEs SAEs, dose reductions, interruptions and discontinuation and assessment of dysgeusia
Exploratory	
CCI CCI CCI CCI CCI	CCI CCI CCI CCI CCI CCI CCI CCI

CCI	CCI

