4.2.9 Analysis Conventions

Continuous data will be summarized in terms of the mean, standard deviation, median, minimum, maximum and number of observations, unless otherwise stated.

The minimum and maximum will be reported to the same number of decimal places as the raw data recorded in the database. The mean and median, will be reported to one more decimal place than the raw data recorded in the database. The standard deviation will be reported to two more decimal places than the raw data recorded in the database. In general, the maximum number of decimal places reported shall be four for any summary statistic.

Categorical data will be summarized in terms of the number of patients providing data at the relevant time point (n), frequency counts and percentages. Any planned collapsing of categories will be detailed in the SAP text and the data displays.

Percentages will be presented to one decimal place. Percentages will not be presented for zero counts. Percentages will be calculated using n as the denominator.

Changes from baseline in categorical data will be summarized using shift tables where appropriate.

Confidence intervals will be presented to one more decimal place than the raw data.

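### The planned taste-questionnaire charts have no screening comparator and no stated denominator, so they cannot separate new or worsened taste change from pre-existing change

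*SAP*

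**What the plan says.** The secondary safety endpoint in SAP section 2 lists adverse events and dose changes and ends with "interruptions and discontinuation and assessment of dysgeusia". The taste questionnaire is one component of that endpoint.

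- **Collection.** Protocol 8.3.12 has site staff complete the taste assessment "at screening for each patient enrolled, and for any patient who reports dysgeusia" in answer to the open question about health problems. For those who report it, "the assessment will be performed at each visit until the adverse event has resolved". SAP 4.12.2 agrees: "A taste assessment questionnaire will be performed at screening and at each study visit when patient reports dysgeusia".
- **Summary.** SAP 4.12.2 states: "A bar-chart will present the worst answers to the main questions after screening". A second chart shows the worst answers on how taste is altered, with no time frame given; where a patient answers in both directions, loss ranks as worse than heightened sensitivity. It adds: "A by-patient listing will also be provided". The section plans no comparison with screening and names no denominator.
- **General conventions.** SAP 4.2.9 states: "Categorical data will be summarized in terms of the number of patients providing data at the relevant time point (n), frequency counts and percentages". It sets percentages on that n, and foresees shift tables for categorical change from baseline where they are appropriate. SAP 4.12 bases safety summaries on the FAS.

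**The concern.** The protocol added this questionnaire because CTCAE grading, which has only two grades for dysgeusia, describes the event poorly. Its value lies in showing what kind of taste change occurs and how far it goes. A chart of worst post-screening answers shows how taste was at its worst on study, not whether it changed. A patient with the same altered taste at screening and afterwards looks the same as a new case.

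The missing denominator adds a second ambiguity. After screening, only patients who report dysgeusia are assessed. A reader cannot tell whether a bar is a count, a share of reporters, or a share of all treated patients. Dysgeusia is the recognised on-target toxicity of this class, so the display will be read closely.

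**Working it through.** The documents give no expected rate, test or sample size for the taste questionnaire, so there is no plan figure to reproduce. The check has three parts.

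**1. Can pre-existing altered taste reach the charts?** Yes.
- Inclusion criterion 4 (Protocol 5.1) requires at least one prior regimen for metastatic disease.
- Exclusion criterion 6 (Protocol 5.2) bars residual adverse events of prior therapy only if they have not resolved to Grade 1 or lower.
- Grade 1 dysgeusia (Protocol 8.3.12) is altered taste without a change in diet.

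Such a patient can enrol, mention the altered taste at a later visit, be assessed, and be charted. The documents do not say how often this happens.

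**2. Is taste treated like the other safety measures?** No. Laboratory grades (SAP 4.12.3), blood pressure (Vital Signs, 4.12.4.1), QTcF (4.12.4.2) and ECOG status (4.12.4.3) each have an explicit shift table from baseline to worst later value. Taste has a screening value for every enrolled patient and no such table.

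**3. Which way could the display err?** Inputs:
- q, the share of patients reporting dysgeusia. Phase 1 treatment-related rates stand in for it: 6/20 = 30% at monotherapy doses up to 2 mg (Protocol 4.4.1.1; 2.3.1.2 gives both 6/20 and, in its dysgeusia paragraph, 5/20 = 25%); 10/25 = 40% over all monotherapy doses (Table 7); 4/8 = 50% at 1.5 mg with nivolumab (Table 11).
- b, the share of reporters whose altered taste was present and unchanged since screening. Not given; assumed 0 to 30%.
- u, the share of non-reporters with a new change they did not report. Not given; assumed 0 to 30%.
- Simplification: every reporter's worst answer shows some alteration.

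True rate of new or worsened change = q(1 - b) + (1 - q)u. Charted rate on the FAS = q. Error = q - true = qb - (1 - q)u.

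| q | b | u | True rate | Charted (FAS) | Error (points) |
|---|---|---|---|---|---|
| 30% | 20% | 0 | 24% | 30% | +6 |
| 30% | 20% | 20% | 38% | 30% | -8 |
| 30% | 30% | 0 | 21% | 30% | +9 |
| 30% | 0 | 30% | 51% | 30% | -21 |
| 50% | 20% | 0 | 40% | 50% | +10 |
| 50% | 20% | 20% | 50% | 50% | 0 |
| 50% | 30% | 0 | 35% | 50% | +15 |
| 50% | 0 | 30% | 65% | 50% | -15 |

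The sign changes at u = qb/(1 - q). With b = 20% that is 0.06/0.70 = 8.6% at q = 30%, and 0.10/0.50 = 20% at q = 50%.

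If the denominator is instead the assessed reporters, each category percentage is 1/q times its FAS value: 4.0-fold at 25%, 3.3-fold at 30%, 2.5-fold at 40% and 2.0-fold at 50%.

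**The case against.** The strongest reply is that incidence is handled elsewhere. SAP 4.12.1 tabulates TEAEs by preferred term and by maximum grade, on the FAS, and counts a pre-existing event only if it worsens. The questionnaire describes dysgeusia in those who report it, so being conditional on reporting is its design. This stands: the charts are not the whole dysgeusia endpoint, and the plan can estimate how often dysgeusia newly occurs or worsens. The TEAE tables do not, however, show whether the questionnaire answers worsened, or in what way.

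Screening answers are not discarded either. The listing excludes no visit, and the general convention permits shift tables. That also stands, but a listing leaves the reader to build the comparison, and 4.12.2 does not invoke the convention.

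A reader might infer that the charts overstate drug-caused taste change. The documents do not support that. The arithmetic gives errors of either sign on the FAS, and overstatement is the likely net result only with a reporters-only denominator. That denominator is itself an inference: 4.2.9 defines n at a time point, which a worst-over-study answer lacks, while 4.12 points to the FAS. Nor do questionnaire data exist only for reporters; at screening everyone enrolled is assessed.

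Finally, the questions and response scale are not reproduced in the documents, so whether every item can be ranked against screening cannot be checked. The SAP does assume that answers can be ranked, since it charts the worst one and gives a tie rule.

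**Conclusion.** The point holds as a gap in a descriptive summary. The taste charts lack a screening comparator and a stated denominator, so they cannot separate new or worsened alteration from alteration present at entry. Omitting screening alone adds q times b to the display: 0 to 9 points at 30% reporting and 0 to 15 at 50%, for the assumed b of 0 to 30%. With 20 patients in an arm (the evaluable target; the enrolled number is redacted), that is up to about 2 of 6 reporters (0.3 × 6 = 1.8) or 3 of 10. Once unreported change is allowed for, the net error on the FAS spans +15 to -21 points, so no direction can be claimed. All of these sizes rest on assumed b and u and on Phase 1 rates standing in for q.

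The consequence is limited. The display involves no test and no between-arm comparison, and efficacy conclusions are unaffected. It is still worth correcting, because nothing else in the plan summarises change in the questionnaire answers.

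**What to change.** In SAP 4.12.2:

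- Add a shift table by arm from the screening answer to the worst post-screening answer, for the main questions and for the type of alteration.
- Use the FAS. Show patients never assessed after screening as 'no dysgeusia reported / not assessed', and give the number assessed.
- Keep both bar charts as supportive, and state the time frame and denominator of each.

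The table resolves the pre-existing component. It cannot recover unreported changes, but the 'not assessed' row makes that gap visible.

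The cost is SAP wording and one programmed output. All the data are already collected, and neither the visit schedule nor the questionnaire changes.
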